#### **4.6.1. Primary Efficacy Variable**

The primary efficacy endpoint is the percent change in LDL-C from baseline to week 12 in the ITT population for alirocumab 150 mg Q2W as compared with placebo in patients with HoFH, using all LDL-C values regardless of adherence to treatment (ITT estimand).

The percent change in LDL-C from baseline to week 12 is defined as:  $100 \times (\text{LDL-C value at week 12} - \text{LDL-C value at baseline}) / \text{LDL-C value at baseline}$ .

#### **4.6.2. Key Secondary Efficacy Variables**

The key secondary efficacy endpoints are:

- The percent change in Apo B from baseline to week 12 (ITT estimand).
- The percent change in non-HDL-C from baseline to week 12 (ITT estimand).
- The percent change in total cholesterol from baseline to week 12 (ITT estimand).
- Proportion of patients with  $\geq 15\%$  reduction in LDL-C at week 12 (ITT estimand).
- Proportion of patients with  $\geq 30\%$  reduction in LDL-C at week 12 (ITT estimand).
- The percent change in Lp(a) from baseline to week 12 (ITT estimand).
- Proportion of patients with  $\geq 50\%$  reduction in LDL-C at week 12 (ITT estimand).
- The percent change in HDL-C from baseline to week 12 (ITT estimand).

- The percent change in fasting TG from baseline to week 12 (ITT estimand).
- The percent change in Apo A-1 from baseline to week 12 (ITT estimand).

#### 4.6.3. Other Secondary Efficacy Variables

The other secondary efficacy endpoints are:

- The percent change in LDL-C from baseline to week 12 in the modified (m)ITT population, using all LDL-C values during the efficacy treatment period (on-treatment estimand).
- The percent change in Apo B, non-HDL-C, TC, Lp(a), HDL-C, fasting TG and Apo A-1 from baseline to week 12 (on-treatment estimand).
- Proportion of patients with  $\geq 15\%$  reduction,  $\geq 30\%$  reduction, and  $\geq 50\%$  reduction in LDL-C at week 12 (on treatment estimand).
- The absolute change in the ratio of Apo B/Apo A-1 from baseline to week 12 (ITT estimand).

The efficacy treatment period is defined as the time from the first double-blind study treatment injection up to 21 days after the last double-blind study treatment injection, or the first open-label alirocumab injection (if applicable), whichever comes first.

### 4.7. Safety Variables

Patient safety will be assessed through the collection of reported adverse events (AEs), clinical laboratory data, vital signs, and ECG. Unless otherwise noted, the baseline value is defined as the last available value before the first dose of double-blind study treatment.

#### 4.7.1. Adverse Events Variables

The period of safety observation starts from the time when the patient gives informed consent and continues into the following periods:

- The PRE-TREATMENT period: defined as the time from the signed informed consent up to the first double-blind study treatment injection.
- The double-blind treatment-emergent adverse event (TEAE) period: defined as the time from the first double-blind study treatment injection up to the day of the last double-blind study treatment injection + 70 days (10 weeks), or up to the day before first dose of open label investigational study drug administration, whichever is earlier.

The double-blind TEAE period will include:

- The TREATMENT period is defined as the time from the first double-blind study treatment injection up to the day of last double-blind study treatment injection + 21 days, as serum concentration of alirocumab >10 µg/mL is expected for approximately 21 days following administration of 150 mg. Further, in previous studies, alirocumab concentrations declining below this concentration also showed a decrease in effect on LDL-C. For patients entering into the open-label period, the treatment period will be truncated at the day before the first dose of open label investigational study drug administration.
- The RESIDUAL TREATMENT period is defined as the time from the day of last double-blind study treatment injection + 22 days up to the day of last double-blind study treatment injection + 70 days (10 weeks), or up to the day before first dose of open label investigational study drug administration, whichever is earlier.
- The open-label treatment-emergent adverse event (TEAE) period is defined as the time from first open label study treatment injection up to the day of the last open-label study treatment injection + 70 days.

The open-label TEAE period will include:

- The TREATMENT period is defined as the time from the first open-label study treatment injection up to the day of last open-label study treatment injection + 21 days.
- The RESIDUAL TREATMENT period is defined as the time from the day of last open-label study treatment injection + 22 days up to the day of last open-label study treatment injection + 70 days (10 weeks).
- The POST-TREATMENT period: defined as starting the day after the end of the respective TEAE periods up to the patient's end of study.

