All patients who meet the inclusion criteria and none of the exclusion criteria will enter the 12-week double-blind treatment period. The first injection of double-blind study drug will occur on day 1 (baseline), and the last injection of double-blind study drug will occur on day 71 (week 10).

Following the completion of the 12-week double-blind treatment period, all patients will enter a 12-week open-label treatment period. The first injection of open-label alirocumab will occur on day 85 (week 12) and the last injection of open-label alirocumab will occur on day 155/week 22. After completion of the 12-week open-label treatment period, all patients who have successfully completed this study may have the opportunity to participate in an additional lipid-lowering clinical trial.

---

Study Duration	This is a 24-week study, excluding the optional 4-week run-in period and the 2-week screening period.
-----------------------	---

Population	The study population will consist of male and female patients, $\geq 18$ years of age diagnosed with HoFH.
-------------------	--

**Sample Size:** Approximately 74 patients

**Target Population:** Males and females  $\geq 18$  years of age diagnosed with HoFH, except patients known to have null/null mutations in both LDLR alleles.

---

Treatment(s)	
Study Drug	Alirocumab 150 mg SC every 2 weeks from day 1 through week 12 (end of double-blind treatment period, last double-blind injection at week 10).
Dose/Route/Schedule:	Regardless of treatment assignment in the double-blind treatment period, all patients will receive open-label alirocumab 150 mg SC Q2W starting at week 12 and continuing through week 24 (last injection in the open-label period at week 22).
Reference Drug	Placebo SC Q2W

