### 8.1.1. Footnotes for the Schedule of Events Table

1. Informed consent/assent will be obtained either at Visit 1a (for patients who need the optional run-in time) or at Visit 1 (for the patients who do not need optional run-in).
2. Injection training will be performed with the patient and/or caregiver during the screening period or at baseline using placebo.
3. After the investigational study drug administration (double-blind and open-label), patients will need to be monitored for 30 minutes.
4. Lipid panel will consist of: total-C, LDL-C, HDL-C, TG, non-HDL-C. Specialty lipid panel will consist of: ApoB, Apo A-1, ratio Apo B/Apo A-1, and Lp(a). Lipid panels should be collected after an approximately 8 hour fast.
5. ECG should be performed before blood samples are collected.
6. On days when a clinic visit coincides with a dosing day, all blood samples (including ADA samples) will be collected immediately prior to LDL apheresis (if applicable) and before the investigational study drug administration, but after study assessments are performed. PK samples will also be used for free and total PCSK9 analysis.
7. Sample should be obtained prior to randomization and will be used to determine HoFH mutation status. Patients on apheresis may collect this during visit 1a.

9. Visit window is  $\pm 3$  days for patients not on apheresis and +1 day for patients on apheresis. Every attempt should be made to ensure all samples are collected immediately prior to LDL apheresis. The timing between the baseline sample collection relative to the most recently completed LDL apheresis procedure should match the timing of the week 12 sample collection relative to the most recently completed LDL apheresis procedure. Depending on the duration between the LDL apheresis procedure and sample collection, the visit window may not apply.

10. This visit is only for patients who do not participate in another lipid-lowering study.

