##### Definitions

For safety variables, the following observation periods are defined:

- The pretreatment period is defined as the time from signing the ICF to before the first dose of double-blind investigational study drug.
- The double-blind TEAE observation period is defined as the time from first dose of double-blind investigational study drug to the last dose of double-blind investigational study drug + 70 days, or up to the day before first dose of open-label investigational study drug administration, whichever is earlier.
- The open-label TEAE observation period is defined as the time from first open-label study treatment administration to the last open-label study treatment administration + 70 days.
- The post-treatment observation period is defined as the time from the day after the end of the respective TEAE periods up to the patient's end of study.
- Pre-treatment AEs are defined as those that developed, worsened, or became serious during the pre-treatment period.
- Double-blind and open-label TEAEs are defined as those that developed, worsened, or became serious during the respective TEAE periods.
- Double-blind and open-label post-treatment AEs are defined as those that developed, worsened, or became serious during the post-treatment period.

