#### 10.4.4.2. Laboratory Data and Vital Signs

The following definitions will be applied to laboratory parameters and vital signs:

- The baseline value is defined as the last available value before first dose of double-blind investigational study drug.
- The PCSA values are defined as abnormal values considered medically important by the sponsor according to predefined criteria/thresholds based on literature review and defined by the sponsor for clinical laboratory tests and vital signs.
- PCSA criteria will determine which patients had at least 1 PCSA during the TEAE period, taking into account all evaluations performed during the TEAE period, including unscheduled or repeated evaluations. The number of all such patients will be the numerator for the PCSA percentage.
- Double-blind treatment period: the treatment period used for quantitative analysis (laboratory results and vital signs) in the double-blind period is defined as the time from the first double-blind dose of the investigational study drug to the last double-blind dose of the investigational study drug + 21 days, or up to the first open-label dose of the investigational study drug, whichever comes first.
- Open-label treatment period: the treatment period used for quantitative analysis (laboratory results and vital signs) in the open-label study period is defined as the time from the first open-label dose of the investigational study drug to the last open-label dose of the investigational study drug + 21 days.

Summary statistics (including mean, median, Q1, Q3, standard error, minimum and maximum) of all laboratory variables and all vital sign parameters (raw data and changes from baseline) will be calculated for each visit, last and worst value assessed during the treatment period, and presented by treatment group. For selected parameters, mean changes from baseline with the corresponding standard error will be plotted over time (at same time points) in each treatment group.

The incidence of PCSAs at any time during the TEAE period will be summarized by treatment group for the double-blind study period, and by all patients and by the as-treated treatment group for the open-label study period, whatever the baseline level and/or according to the following baseline categories:

- Normal/missing
- Abnormal according to PCSA criterion or criteria

For laboratory parameters for which PCSA criterion is not defined, similar table(s) using the normal range could be provided.

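### The double-blind safety periods close the day before the pre-dose Week 12 assessments, so the ECG, abnormality and last/worst-value tables lose Week 12

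*SAP*

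**What the plan says.** SAP 4.7.1 defines two double-blind periods that drive most safety tables. The treatment period runs to the last double-blind injection plus 21 days, but for patients entering the open-label phase "the treatment period will be truncated at the day before the first dose of open label investigational study drug administration". The TEAE period runs to the last double-blind injection plus 70 days, "or up to the day before first dose of open label investigational study drug administration, whichever is earlier". The protocol's TEAE definition (10.4.4.1) has the same cut: "up to the day before first dose of open-label investigational study drug administration, whichever is earlier".

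Two other definitions place the boundary at the injection itself. Protocol 10.4.4.2 ends the treatment period for quantitative laboratory and vital-sign analysis at last dose plus 21 days, "or up to the first open-label dose of the investigational study drug, whichever comes first". SAP 4.6.3 ends the efficacy treatment period at 21 days after the last double-blind injection, "or the first open-label alirocumab injection (if applicable), whichever comes first". The Week 12 analysis windows in SAP Tables 1a and 1b include the day of the first open-label injection.

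Protocol Table 1 puts the first open-label injection at Visit 6, Day 85. On dosing-day visits "all blood samples (including ADA samples) will be collected immediately prior to LDL apheresis (if applicable) and before the investigational study drug administration", and those samples follow the other study assessments. Also, "ECG should be performed before blood samples are collected". The Visit 6 assessments therefore come before the open-label dose on the same calendar day.

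Outputs tied to the TEAE period are the ECG table (SAP 5.7.4), all PCSA counts (5.7, 5.7.2, 5.7.3, 5.8), the ALT-increase and eDISH displays (5.7.2) and one of the two hepatitis C seroconversion counts (5.7.2). Last and worst on-treatment values use the treatment period, with an explicit reference to 4.7.1 (SAP 5.7).

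**The concern.** A cut at the day before dosing suits events recorded by date, where an event on the dosing day cannot safely be called pre-dose. It does not suit measurements that the protocol requires before the dose. Here it removes the end-of-double-blind visit from the tables meant to summarise the double-blind phase.

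That phase is the only placebo-controlled safety comparison in the study. SAP 5.7 counts in a PCSA denominator only patients assessed at least once in the TEAE period, so denominators shrink along with the numerators. What remains is also selected: patients who stop early have an unscheduled visit with end-of-double-blind assessments (Protocol 7.4.2), and that visit can fall inside the period when a completer's Week 12 visit does not.

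The lost values have no good alternative home. Assigned by date, a placebo patient's pre-dose abnormality on Day 85 could be counted as emergent on open-label alirocumab, because SAP 5.7 keeps the double-blind baseline for open-label safety analyses. Assigned by time, it falls in the double-blind post-treatment period, which begins the day after the TEAE period ends.

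**Working it through.** **Inputs**

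- Last double-blind injection: Day 71, week 10 (Protocol 5.1).
- First open-label injection: Day 85, week 12, at Visit 6 (Protocol synopsis and Table 1).
- Visit 6 assessments precede that injection (Protocol 8.1.1, footnotes 5 and 6).
- Scheduled assessments by visit: Protocol Table 1.

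**Reproducing the study days.** Study day = 7 × week + 1. Week 10 gives 7 × 10 + 1 = 71 and week 12 gives 7 × 12 + 1 = 85, as the protocol states.

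**Period ends on the planned schedule**

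- SAP treatment period: min(71 + 21, 85 − 1) = min(92, 84) = Day 84.
- SAP and protocol TEAE period: min(71 + 70, 85 − 1) = min(141, 84) = Day 84.
- Protocol 10.4.4.2 treatment period: min(71 + 21, 85) = Day 85.
- SAP Week 12 window: Day 71 (Table 1a) or Day 78 (Table 1b) to min(98, 85) = Day 85.

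Moving the visit does not help while the injection is given at it. A visit on Day 82 gives a cut at Day 81; a visit on Day 88 gives a cut at Day 87. The results are kept only if the first open-label injection comes at least one day after the assessments, or if the patient does not enter the open-label phase and the results fall within the 21-day or 70-day limit.

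**Scheduled double-blind post-baseline results kept, for a patient starting open-label at Visit 6**

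| Output | Scheduled weeks | Kept, cut at Day 84 | Kept, cut at the injection |
|---|---|---|---|
| ECG table | 12 | 0 of 1 | 1 of 1 |
| Weight PCSA and last/worst | 12 | 0 of 1 | 1 of 1 |
| hs-CRP PCSA | 12 | 0 of 1 | 1 of 1 |
| Hepatitis C, TEAE-only count | 12 | 0 of 1 | 1 of 1 |
| Laboratory PCSA, ALT increase, eDISH, laboratory last/worst | 8, 12 | 1 of 2 | 2 of 2 |
| Blood pressure and heart rate PCSA and last/worst | 4, 8, 10, 12 | 3 of 4 | 4 of 4 |

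**PCSA denominators for weight and hs-CRP, both arms together.** The documents do not say how many patients will have a Week 12 result without starting open-label that day. Taking 0%, 5% or 10% of 74 as an assumed range: 74 × 0.00 = 0; 74 × 0.05 = 3.7, about 4; 74 × 0.10 = 7.4, about 7. The intended denominator is up to 74.

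**Not affected.** By-visit laboratory and vital-sign summaries run to last dose plus 21 days, and Day 85 is before Day 92. The hepatitis C count over all post-baseline data, the EQ-5D Week 12 cumulative distribution, and the primary and key secondary lipid endpoints do not depend on these periods.

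**Undetermined.** The by-visit hs-CRP summary (SAP 5.8) and the EQ-5D item and utility tables (SAP 5.12) are restricted to a treatment period that those sections do not define. If it is the 4.7.1 period, Week 12 is lost there too.

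**The case against.** The strongest objection concerns attribution. The ECG, PCSA, ALT-increase, eDISH and TEAE-only hepatitis C outputs all rest on the TEAE period, whose cut is the protocol's own (10.4.4.1), and Protocol 10.4.4.2 itself specifies PCSA over that period. For these tables the SAP follows the protocol. Only the treatment-period truncation, which governs last and worst values, departs from Protocol 10.4.4.2. This is right, and it means both documents need attention; it does not restore the missing data.

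Second, analysis windows and the efficacy period serve other purposes, so including Day 85 there does not strictly contradict excluding it from a safety period. That is fair. The firm conflict is between Protocol 10.4.4.2 and SAP 4.7.1. The windows, and the SAP's treatment of same-day values as pre-dose on Day 1 (10.2, 6.4), show that the plan elsewhere regards such values as belonging before the dose.

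Third, SAP 4.7.1 starts the open-label period at the injection, so counting a pre-dose value as open-label requires assignment by date, which the plan does not state. That also stands. Applying time instead still leaves the value outside the double-blind period.

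Fourth, the loss is not total. Early-discontinuation visits and repeat tests can supply in-period values, by-visit summaries keep Week 12, and the Hy's law listing is not stated to be limited to the TEAE period. These soften the effect but do not supply scheduled Week 12 results for completers.

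Finally, separate boundaries for events and measurements could place a Day 85 laboratory rise in the double-blind phase while the same finding, reported as an adverse event dated Day 85, falls outside it. This is a real but small cost.

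**Conclusion.** The concern holds. As written, for every patient who takes the first open-label injection at Visit 6, which is the planned schedule, the Week 12 safety assessments fall one day outside the double-blind treatment and TEAE periods. No rule in either document brings them back. The ECG, weight PCSA and hs-CRP PCSA tables have no scheduled double-blind result, and laboratory PCSA, ALT-increase and eDISH outputs rest on Week 8 alone.

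The counts follow from the schedule. The remaining denominators of about 0 to 7 out of 74 rest on the assumed 0% to 10% range and ignore unscheduled values. The by-visit hs-CRP and EQ-5D effects depend on an undefined phrase.

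Only descriptive safety and exploratory outputs are touched, and no efficacy conclusion changes. It should be fixed because the affected tables are the controlled safety evidence. The treatment-period departure from Protocol 10.4.4.2 is also undeclared: SAP 1.2.3 lists only the new-onset-diabetes change.

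**What to change.** In SAP 4.7.1, for ECG, laboratory tests, vital signs and weight, hs-CRP, hepatitis C and EQ-5D:

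- End the double-blind treatment and TEAE periods at the date and time of the first open-label injection, the boundary already in Protocol 10.4.4.2 and SAP 4.6.3.
- Assign pre-dose assessments on that day, and untimed values from the Week 12 visit, to the double-blind period. SAP 6.4 already does the equivalent for untimed values on the first double-blind dosing day.
- Start the open-label period for these measures after that injection.

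Keep the day-before rule for adverse events recorded by date, and say in the table notes that the two boundaries differ. Align Protocol 10.4.4.1 or list the change in SAP 1.2.3. State in SAP 5.8 and 5.12 whether the treatment period meant there is the one in 4.7.1. While editing, reconcile SAP 5.6.1.2 with Appendix 10.7, which end the on-treatment period of the pattern mixture analysis on the day of the first open-label injection and on the day before it, respectively.

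The cost is SAP wording, one programming rule with a tie-break for untimed values, and one protocol edit or SAP entry. No new data are needed. The change should be in place before the first-step database lock.

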#### **4.3. Prior and Concomitant Medications**

All medications taken from the time of informed consent/assent to the final study visit, including medications that were started before the study and are ongoing during the study, are to be reported in Concomitant Medications case report form page.

All medications will be dictionary coded using the World Health Organization-Drug Dictionary (WHO-DD) to both an anatomic category and a therapeutic category, with the version in effect at the time of database lock for the analysis. Drug names will be matched to respective

Anatomical-Therapeutic-Chemical (ATC) classification, although a drug can be matched to more than one ATC classification (i.e. patients can be counted in several categories for the same medication). Definitions for deriving prior medications and concomitant medications are described below, with the understanding that a given medication can be simultaneously classified both as a prior and concomitant medication.

- Prior medications are any medications the patient used within the time period between 3 months prior to the screening visit up to the day before first study treatment administration. Prior medications can be discontinued before first treatment administration or can be ongoing during the treatment phase.
- Double-blind period concomitant medications are defined as any treatments received by the patient concomitantly with the double-blind study treatment, specifically from the first day of double-blind study treatment administration to the last day of double-blind study treatment +70 days (for patients who do not continue into the open-label period). For patients entering the open-label period, concomitant medications will be truncated at the day before the first open-label study treatment administration.
- Open-label period concomitant medications are defined as any treatments received by the patient concomitantly with the open-label study treatment, specifically from the first day of open-label study treatment administration to the last day of open-label study treatment +70 days.
- Double-blind period post-treatment medications are those medications received by the patient during the time period starting from 71 days after the last double-blind study treatment injection and ending when the patient completes the study or begins treatment in the open-label period (whichever comes first) as applicable.

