#### 4.7.1.3. Events Causing Death

The observation periods for patient deaths are per the observation periods defined above.

- Death on-treatment: deaths occurring during the respective TEAE period (double-blind or open-label),
- Death post-treatment: deaths occurring during the respective post-treatment period (double-blind or open-label).

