##### **5.7.1.1. Patient Deaths**

The following summaries of deaths will be generated.

- Number (%) of patients who died by study period (TEAE and post-treatment in both the double-blind and open-label periods);
- Deaths in nonrandomized patients or randomized but not treated patients;
- TEAEs leading to death (death as an outcome on the AE CRF page, as reported by the Investigator) by (at least) SOC (sorted by internationally agreed order), and PT (sorted by decreasing frequency, showing the number (n) and percentage (%) of patients) for both the double-blind and open-label study periods.

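### The double-blind post-treatment period has no stop at the first open-label injection, so in the final safety analysis events on open-label alirocumab also fall in the double-blind post-treatment summaries, including the placebo column

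*SAP*

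**What the plan says.** **Period definitions.** In SAP 4.7.1 the double-blind TEAE period closes 70 days after the last double-blind injection, "or up to the day before first dose of open label investigational study drug administration, whichever is earlier". The open-label TEAE period is the "time from first open label study treatment injection up to the day of the last open-label study treatment injection + 70 days". A single sentence then covers what follows both: "The POST-TREATMENT period: defined as starting the day after the end of the respective TEAE periods up to the patient's end of study". Protocol 10.4.4.1 (Definitions) has the same structure, with a post-treatment period "from the day after the end of the respective TEAE periods up to the patient's end of study".

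**Use of the periods.** SAP 4.7.1.1 names double-blind and open-label post-treatment AEs as separate classes. SAP 4.7.1.3 defines post-treatment deaths as "deaths occurring during the respective post-treatment period (double-blind or open-label"). SAP 5.7.1 tabulates post-treatment AEs and SAEs by system organ class and preferred term, and SAP 5.7.1.1 asks for the "Number (%) of patients who died by study period (TEAE and post-treatment in both the double-blind and open-label periods"). Protocol 10.4.4.1 also asks for post-treatment AE and death summaries in both study periods. SAP 5.7 presents the double-blind period by alirocumab and placebo.

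**A parallel rule.** SAP 4.3 starts double-blind post-treatment medications 71 days after the last double-blind injection, "ending when the patient completes the study or begins treatment in the open-label period (whichever comes first").

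**First-step rules.** SAP section 7 makes the post-treatment period not applicable to patients who are ongoing at the cut-off. It limits post-treatment AE analyses to patients who had completed or prematurely stopped treatment by then.

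**The concern.** The double-blind TEAE, treatment and residual treatment periods in SAP 4.7.1 are all cut at the start of open-label dosing. The post-treatment period for AEs and deaths is not. Once open-label dosing ends the double-blind TEAE period, the next day is both the first day on open-label alirocumab and, by the written rule, the first day of double-blind post-treatment.

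A reader takes a double-blind post-treatment table to describe what happens after double-blind drug has worn off. Under this rule it would mostly hold events that occurred on open-label alirocumab. The patients randomized to placebo are the awkward case: their events on active drug would sit under placebo. The same events would appear again, correctly, as open-label TEAEs. Medications and AEs carrying the same period label would also cover different time windows in the same patient.

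**Working it through.** This is interval arithmetic on the documents' own study days.

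**Inputs.** Last double-blind injection Day 71, first open-label injection Day 85 and last open-label injection Day 155 (Protocol 5.1); end-of-study call Day 225 for patients not joining another lipid-lowering study (SAP 2.3); about 74 patients at 2:1, so about 49 alirocumab and 25 placebo (SAP 2.1).

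**The plan's own figure.** SAP 2.3 says the Day 225 call corresponds to 70 days of follow-up: 155 + 70 = 225. It reproduces.

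**Formulas.**
- Double-blind TEAE end = min(last double-blind injection + 70, first open-label injection − 1)
- Double-blind post-treatment = from double-blind TEAE end + 1 to end of study
- Open-label TEAE = from first open-label injection to min(last open-label injection + 70, end of study)

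**On-schedule patient.**
- Double-blind TEAE end = min(71 + 70, 85 − 1) = min(141, 84) = Day 84
- Double-blind post-treatment = Days 85 to 225, which is 225 − 85 + 1 = 141 days
- Open-label TEAE = Day 85 to min(225, 225), also 141 days
- Overlap: 141 of 141 days. The two windows are identical.

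**Other cases.**

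| Patient | Double-blind post-treatment as written | Overlap with open-label TEAE | After adding the stop |
|---|---|---|---|
| Joins another study (assumed end of study Day 169) | Days 85–169 | 85 of 85 open-label TEAE days | empty |
| Starts open label late (illustration: first injection Day 150, last Day 220, end of study Day 290) | Days 142–290 | 141 of 141 open-label TEAE days | Days 142–149 (8 days), overlap 0 |
| Never enters open label, last dose Day 71, end of study Day 225 | Days 142–225 (84 days) | none | unchanged |

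In each case with open-label entry, the open-label TEAE period up to end of study lies wholly inside the double-blind post-treatment period. The stop reduces the overlap to zero.

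**Exposure at the first step.** The cut-off is the date of the last week 12 visit, which is Day 85 for the last patient. An on-schedule patient randomized k days before the last patient is at study day 85 + k on that date, and reaches the week 24 visit (Day 169) if k is at least 169 − 85 = 84. So patients randomized at least 84 days before the last one would normally have finished open label by the cut-off. The section 7 rule for ongoing patients does not remove them.

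**The case against.** **A sequential reading.** SAP 4.7.1 describes safety observation as moving from one period into the next and gives one post-treatment sentence. *Respective* could mean the TEAE period that comes last for that patient: open-label for those who enter it, double-blind for the rest. Nothing would then overlap. But neither document says this, and it fits poorly with SAP 4.7.1.3, which attaches a post-treatment period to each of the two phases. SAP 4.3 shows that the SAP writes the stop explicitly when it wants one.

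**Exclusive AE classes.** SAP 5.7.1 and 6.4 sort AEs into pre-treatment, treatment-emergent or post-treatment, with treatment-emergent as the default. Those rules are written for incomplete onset dates. They do not settle an event with a known date that falls inside two defined periods.

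**SAP section 7.** This objection stands in part. Ongoing patients are those without an end-of-treatment visit, double-blind or open-label, at the cut-off. A patient still in open label can therefore be read as having no post-treatment period at the first step. A reader might infer from the definition alone that every open-label event is duplicated in both analyses. The documents do not support that for the first step, and section 7 sets no such limit for the second.

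**Limited reach.** This stands. SAP 5.7.1 puts the main focus on TEAEs, and both TEAE periods are cleanly bounded. The SAP 4.3 rule and the truncations in SAP 4.7.1 suggest that a stop was intended, so this is a drafting gap rather than a chosen method. A programmer might add the stop unprompted, but that would be an unrecorded departure from the written plan.

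**Conclusion.** As written, for a patient who enters open label the double-blind post-treatment period contains the whole open-label TEAE period up to end of study: 141 of 141 days on schedule. Open label is mandatory, so the overlap concerns nearly all of the approximately 74 patients. That counts patient time; the number of misplaced events depends on how many occur. In the second-step analysis, open-label AEs, SAEs and deaths would also enter the double-blind post-treatment summaries under both arms. At the first step this holds at least for patients who had completed or stopped open label by the cut-off.

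Two stronger conclusions might be drawn. One is that the randomized safety comparison is contaminated. It is not: the double-blind TEAE period closes before open-label dosing, safety summaries are descriptive, and no TEAE table, efficacy result or alpha changes. The other is a particular false rate under placebo. One open-label death in a former placebo patient would show as 1/25 = 4%, but that is only an illustration; the documents project no such event.

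The conclusion rests on the literal wording of the two definitions and the scheduled days. The Day 169 end of study and the late open-label start are assumptions, and the conclusion does not depend on them. A stated rule gives a mislabelled table, and the correction is simple enough that it should be made.

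**What to change.** In SAP 4.7.1 and Protocol 10.4.4.1, define the double-blind post-treatment period as running from the day after the end of the double-blind TEAE period to the earlier of end of study or the day before the first open-label injection. State that it is empty for a patient whose double-blind TEAE period was ended by open-label dosing. This follows the form SAP 4.3 already uses for medications, and the AE and death classes in SAP 4.7.1.1 and 4.7.1.3 then need no change.

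The cost is one clause in each document and the matching line in the period derivation. No new data are needed, and patients who never enter open label are classified as before. Until the protocol text is aligned, the difference can be listed in SAP 1.2.3, which already records departures from the protocol.
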